7.4. Gilead Reporting Requirements

Depending on relevant local legislation or regulations, including the EU Clinical Trials Directive (2001/20/EC) and relevant updates, and other country-specific legislation or regulations, Gilead may be required to expedite to worldwide regulatory agencies reports of SAEs, SADRs, or suspected unexpected serious adverse reactions (SUSARs). In accordance with the EU Clinical Trials Directive (2001/20/EC), Gilead or a specified designee will notify worldwide regulatory agencies and the relevant IEC in concerned Member States of applicable SUSARs as outlined in current regulations.

Assessment of expectedness for SAEs will be determined by Gilead using reference safety information specified in the investigator's brochure or relevant local label as applicable.

All investigators will receive a safety letter notifying them of relevant SUSAR reports associated with any Tenofovir DF treatment. The investigator should notify the IEC of SUSAR reports as soon as is practical, where this is required by local regulatory agencies, and in accordance with the local institutional policy.

7.5. Toxicity Management

All clinical toxicities and/or abnormal laboratory findings should be investigated for etiology and graded according to the uniform guidelines detailed in [Appendix 5](#). The Gilead Sciences Medical Monitor is available for consultation on all medical and toxicity-related issues and may be contacted as shown below:

Gilead Sciences Medical Monitor	Name:	[name]
	Telephone:	PPD
	Mobile:	PPD
	Fax:	PPD
	Email:	PPD

- All clinical and clinically significant laboratory toxicities will be managed according to uniform guidelines detailed in [Appendix 5](#).
- Grade 3 and 4 clinically significant laboratory abnormalities should be confirmed by repeat testing within 3 calendar days of receipt of results and before drug discontinuation, unless such a delay is not consistent with good medical practice.
- Clinical events and clinically significant laboratory abnormalities will be graded according to the GSI Grading Scale for Severity of Adverse Events and Laboratory Abnormalities ([Appendix 4](#)).
- When restarting Tenofovir DF following resolution of the adverse event, the drug should be restarted at full dose or modified dose that is dependent upon discussion with the Gilead Sciences Medical Monitor.
- Any recurrence of the Tenofovir DF-related Grade 3 or 4 clinical or clinically significant laboratory adverse event following dose interruption mandates permanent discontinuation of drug.
- Any questions regarding toxicity management should be directed to the Gilead Sciences Medical Monitor.

7.5.1. Grades 1 and 2 Laboratory Abnormality or Clinical Event

- Continue Tenofovir DF at the discretion of the investigator.

7.5.2. Grade 3 Laboratory Abnormality or Clinical Event

- For Grade 3 clinically significant laboratory abnormality or clinical event, Tenofovir DF may be continued if the event is considered to be unrelated to drug.
- For a Grade 3 clinical event, or clinically significant laboratory abnormality confirmed by repeat testing, that is considered to be related to Tenofovir DF, drug should be withheld until the toxicity returns to \leq Grade 2.

- If a laboratory abnormality recurs to \geq Grade 3 following restarting Tenofovir DF and is considered related to Tenofovir DF, then Tenofovir DF should be permanently discontinued and the subject managed according to local practice. Recurrence of laboratory abnormalities considered unrelated to Tenofovir DF may not require permanent discontinuation.

7.5.3. Grade 4 Laboratory Abnormality or Clinical Event

For a Grade 4 clinical event or clinically significant Grade 4 laboratory abnormality confirmed by repeat testing that is considered related to Tenofovir DF, Tenofovir DF should be permanently discontinued and the subject managed according to local practice. The subject should be followed as clinically indicated until the laboratory abnormality returns to baseline or is otherwise explained, whichever occurs first. A clinically significant Grade 4 laboratory abnormality that is not confirmed by repeat testing should be managed according to the algorithm for the new toxicity grade.

Tenofovir DF may be continued without dose interruption for a clinically non-significant Grade 4 laboratory abnormality (e.g., Grade 4 CPK after strenuous exercise, or triglyceride elevation that is non-fasting or that can be medically managed) or a clinical event considered unrelated to Tenofovir DF.

7.5.4. Management of Elevated Serum Creatinine and Decreased Creatinine Clearance

- Glomerular filtration rate (estimated creatinine clearance) will be calculated at each visit using the Schwartz Formula for subjects ages 12–17 as follows:

$$\text{Schwartz Formula (mL/min/1.73 m}^2\text{)} = k \times L/\text{Scr}$$

[(k is a proportionality constant, for adolescent females \geq 12 years old is 0.55; and for adolescent males \geq 12 years old is 0.70); L is height in centimeters (cm); and Scr is serum creatinine (mg/dL)]

- If creatinine clearance decreases to < 50 mL/min/1.73 m² (confirmed) at any time during the study, Tenofovir DF should be permanently discontinued, followed by 24 weeks of monthly monitoring in treatment-free follow up if alternative HBV therapy is not initiated.
- Subjects with estimated creatinine clearance < 70 mL/min/1.73 m² and serum creatinine increased ≥ 0.5 mg/dL above baseline should have the serum creatinine and creatinine clearance confirmed by repeating testing within three calendar days of receipt of results and before Tenofovir DF discontinuation, unless such a delay is not consistent with good medical practice.

- Subjects with confirmed estimated creatinine clearance $< 70 \text{ mL/min/1.73 m}^2$ and serum creatinine increased $\geq 0.5 \text{ mg/dL}$ above baseline should have Tenofovir DF discontinued, and the subject should be followed weekly for two weeks. After two weeks, if the estimated creatinine clearance is $\geq 70 \text{ mL/min/1.73 m}^2$, Tenofovir DF may be resumed, with monitoring as described below. If the estimated clearance remains $< 70 \text{ mL/min/1.73 m}^2$, Tenofovir DF should be permanently discontinued, followed by 24 weeks of monthly monitoring in treatment-free follow up if alternative HBV therapy is not initiated.
- The serum creatinine and estimated creatinine clearance should be rechecked within two weeks after restarting treatment to ensure that the subject has stabilized. Once this has been determined, the subject should be evaluated at regularly scheduled study visits.
- If creatinine clearance decreases to $< 70 \text{ mL/min/1.73 m}^2$ (confirmed) following restarting Tenofovir DF treatment, Tenofovir DF should be permanently discontinued, followed by 24 weeks of monthly monitoring in treatment-free follow up if alternative HBV therapy is not initiated.

7.5.5. Management of Reduced Serum Phosphate

If serum phosphate is confirmed to be $< 3.0 \text{ mg/dl}$ (0.96 mmol/l) in any paediatric patient receiving Tenofovir DF, renal function should be re-evaluated within one week, including measurements of blood glucose, blood potassium and urine glucose concentrations. If renal abnormalities are suspected or detected then consultation with a nephrologist should be obtained to consider interruption of Tenofovir DF treatment.

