6.4.1. Group 1: Week 4 Assessments

The following evaluations will be performed at Week 4 unless otherwise specified. Study visits are to be completed ± 7 days of the protocol-specified visit date, based on the Baseline Visit. Week 4 assessments are outlined in the following section (Section 6.4.4). Group 2 subjects will follow local standard of care for renal monitoring and AE collection.

The following assessments and procedures will be performed and recorded on CRFs:

- Changes in medical status or symptoms from prior visit

- Body weight and height
- Blood samples for:
 - Serum renal chemistry (creatinine, glucose, creatinine clearance (calculated), magnesium, bicarbonate, chloride, potassium, sodium), fasting required
- Urinalysis (protein, glucose, creatinine, phosphate, bicarbonate, blood, calcium) , fasting required
- Assessment of medication adherence
- Review of bone and renal AEs and any associated medical management
- Tenofovir DF dispensing and instructions on appropriate dosing and administration
- Concomitant medications (including dietary supplements such as calcium, vitamin D, phosphorus)

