6.4.2. Group 1: Week 12 and 36 Assessments

Study Visit for Weeks 12 and 36 should be completed \pm 7 days of the protocol-specified visit date, based on the Baseline Visit. Group 2 subjects will follow local standard of care for renal monitoring and AE collection. The following assessments and procedures will be performed and recorded on CRFs:

- Complete physical examination including, vital signs, body weight and height
- Group 1: Urinalysis (protein, glucose, creatinine, phosphate, bicarbonate, blood, calcium), fasting required
- Blood samples for:
 - Group 1: Serum renal chemistry (creatinine, glucose, creatinine clearance (calculated), magnesium, bicarbonate, chloride, potassium, sodium), fasting required
 - Plasma HBV DNA (PCR method)
- Review of bone and renal AEs and any associated medical management
- Concomitant medications (including dietary supplements such as calcium, vitamin D, phosphorus)
- Assessment of medication adherence
- Tenofovir DF dispensing and instructions on appropriate dosing and administration

- Screening for pregnancy (urine screen)

Subjects who discontinue the study prior to the Week 12 or 36 Visit will complete all Week 12 or 36 assessments and procedures at an Early Drug Discontinuation Visit, to be completed within 72 hours of last dose of Tenofovir DF. Subjects who have received at least one dose of Tenofovir DF and permanently discontinue treatment will be followed for 24 weeks off treatment or up to initiation of an alternative treatment regimen, whichever occurs first.

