6.4.3. Groups 1 and 2: Week 24 and 72 Assessments

Study Visit for Weeks 24 and 72 should be completed \pm 7 days of the protocol-specified visit date, based on the Baseline Visit. Group 2 subjects will follow local standard of care for renal monitoring. The following assessments and procedures will be performed and recorded on CRFs:

- Complete physical exam including vital signs, body weight and height
- Blood samples for:
 - Plasma HBV DNA (for PCR)
 - HBV serology (HBeAg and HBsAg; anti-HBe and anti-HBs (if HBsAg negative))
 - Hematology (CBC with differential and platelets, PT/INR)
 - Group 1: Serum renal chemistry (glucose, creatinine, creatinine clearance (calculated), magnesium, bicarbonate, chloride, potassium, sodium), fasting required
 - Liver chemistry (ALT, ALP, AST, total and direct bilirubin, total protein, albumin, GGT, LDH, CK), fasting required
 - Group 1 Only: Serum bone chemistry (calcium, phosphorus, 1,25 hydroxy vitamin D, PTH, osteocalcin, bone alkaline phosphatase, N and C telopeptides), fasting required
- Group 1 Only: DEXA (+/- 14 days of the Week 24 or Week 72 visit) scan of spine and whole body
- Group 1: Urinalysis (glucose, protein, creatinine, phosphate, bicarbonate, blood, calcium), fasting required
- Review of bone and renal AEs and any associated medical management
- Concomitant medications (including dietary supplements such as calcium, vitamin D, phosphorus)
- Assessment of medication adherence

- Tenofovir DF dispensing and instructions on appropriate dosing and administration
- Screening for pregnancy (urine screen)

Subjects who discontinue the study prior to the Week 24 or 72 Visit will complete all Week 24 or 72 assessments and procedures at an Early Drug Discontinuation Visit, to be completed within 72 hours of last dose of Tenofovir DF. Subjects who have received at least one dose of Tenofovir DF and permanently discontinue treatment will be followed for 24 weeks off treatment or up to initiation of an alternative treatment regimen, whichever occurs first.

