6.4.5. Groups 1 and 2: Week 60 and 84 Assessments

Study Visit for Weeks 60 and 84 should be completed \pm 7 days of the protocol-specified visit date, based on the Baseline Visit. Group 2 subjects will follow local standard of care for renal monitoring. The following assessments and procedures will be performed and recorded on CRFs:

- Complete physical exam including vital signs, body weight and height
- Blood samples for:
 - Plasma HBV DNA (for PCR)
 - Group 1: Serum renal chemistry (glucose, creatinine, creatinine clearance (calculated), magnesium, bicarbonate, chloride, potassium, sodium), fasting required
- Group 1: Urinalysis (glucose, protein, creatinine, phosphate, bicarbonate, blood, calcium), fasting required
- Review of bone and renal AEs and any associated medical management
- Concomitant medications (including dietary supplements such as calcium, vitamin D, phosphorus)
- Assessment of medication adherence
- Tenofovir DF dispensing and instructions on appropriate dosing and administration
- Screening for pregnancy (urine screen)

Subjects who discontinue the study prior to the Week 60 or 84 Visit will complete all Week 60 or 84 assessments and procedures at an Early Drug Discontinuation Visit, to be completed within 72 hours of last dose of Tenofovir DF. Subjects who have received at least one dose of

Tenofovir DF and permanently discontinue treatment will be followed for 24 weeks off treatment or up to initiation of active treatment, whichever occurs first.

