Appendix 2. Study Procedures Table

Study Procedures	Study Week												
	Screening	Baseline	4	12	24	36	48	60	72	84	96	30d Follow-Up	
Written Informed Consent	x												
Medical History	x												
HBV DNA		x		x	x	x	x	x	x	x	x		
HBV serology	x	x			x		x		x		x		
HCV, HDV, HIV testing		x											
HBV genotype		x											
DEXA, Group 1		x			x		x		x			x	
DEXA, Group 2		x					x					x	
Serum bone chemistry, Group 1		x			x		x		x			x	
Serum bone chemistry, Group 2		x					x					x	
Serum renal chemistry, Group 1	x	x	x	x	x	x	x	x	x	x	x	x	
Serum renal chemistry, Group 2*	x	x										x	
Liver chemistry	x	x			x		x		x			x	
Hematology		x			x		x		x			x	
Urinalysis, Group 1 (see * for Group 2)	x	x	x	x	x	x	x	x	x	x	x	x	
Complete physical examination	x	x		x	x	x	x	x	x	x	x	x	
Changes in medical status or symptoms, Group 1 (see † for Group 2)		x	x										
Drug dispensed and accountability/Concomitant medications		x	x	x	x	x	x	x	x	x	x	x	
Assess for AE, including renal and bone events (see † for Group 2)		x	x	x	x	x	x	x	x	x	x	x	x
Pregnancy test	x	x		x	x	x	x	x	x	x	x	x	

[figure not shown]
* Group 2 will follow local standard of care for renal monitoring, which may include the Tenofovir DF SmPC recommended screening intervals

† Group 2 subjects may have changes in medical status or symptoms and new AE assessed upon return for renal monitoring, as per standard of care and within the 12 week intervals of scheduled physical examinations

Definitions:

HBV serology	HBeAg, HBsAg, anti-Hbe, anti-HBs
Serum bone chemistry	calcium, phosphorus, 25-hydroxy and 1, 25 dihydroxyvitamin, PTH, osteocalcin, bone alkaline phosphatase, N and C telopeptides
Serum renal chemistry	glucose, creatinine, creatinine clearance (calculated), magnesium, bicarbonate, chloride, potassium, sodium
Liver chemistry	alanine aminotransferase (ALT), alkaline aminophosphatase (ALP), aspartate aminotransferase (AST), total and direct bilirubin, total protein, albumin, gamma glutamyl transpeptide (GGT), LDH, CK
Hematology	PT/INR, complete blood count (CBC) with differential, platelets
Urinalysis	glucose, protein, creatinine, phosphate, bicarbonate, blood, calcium
Complete physical exam	includes vital signs, body weight and height

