Hypocalcemia (corrected for albumin if appropriate*) Adult and Pediatric ≥ 7 Days Infant, < 7 Days	7.8 to 8.4 mg/dL 1.94 to 2.10 mmol/L 6.5 to 7.5 mg/dL 1.61 to 1.88 mmol/L	7.0 to < 7.8 mg/dL 1.74 to < 1.94 mmol/L 6.0 to < 6.5 mg/dL 1.49 to < 1.61 mmol/L	6.1 to < 7.0 mg/dL 1.51 to < 1.74 mmol/L 5.5 to < 6.0 mg/dL 1.36 to < 1.49 mmol/L	< 6.1 mg/dL < 1.51 mmol/L < 5.5 mg/dL < 1.36 mmol/L
Hypercalcemia (corrected for albumin if appropriate*) Adult and Pediatric ≥ 7 Days Infant, < 7 Days	>ULN to 11.5 mg/dL >ULN to 2.88 mmol/L 11.5 to 12.4 mg/dL 2.86 to 3.10 mmol/L	> 11.5 to 12.5 mg/dL > 2.88 to 3.13 mmol/L > 12.4 to 12.9 mg/dL > 3.10 to 3.23 mmol/L	> 12.5 to 13.5 mg/dL > 3.13 to 3.38 mmol/L > 12.9 to 13.5 mg/dL > 3.23 to 3.38 mmol/L	> 13.5 mg/dL > 3.38 mmol/L > 13.5 mg/dL > 3.38 mmol/L
Hypocalcemia (ionized)	3.0 mg/dL to < LLN 0.74 mmol/L to < LLN	2.5 to < 3.0 mg/dL 0.62 to < 0.74 mmol/L	2.0 to < 2.5 mg/dL 0.49 to < 0.62 mmol/L	< 2.0 mg/dL < 0.49 mmol/L
Hypercalcemia (ionized)	> ULN to 6.0 mg/dL > ULN to 1.50 mmol/L	> 6.0 to 6.5 mg/dL > 1.50 to 1.63 mmol/L	> 6.5 to 7.0 mg/dL > 1.63 to 1.75 mmol/L	> 7.0 mg/dL > 1.75 mmol/L
Hypomagnesemia	1.40 to <LLN mg/dL 1.2 to <LLN mEq/L 0.58 to <LLN mmol/L	1.04 to < 1.40 mg/dL 0.9 to < 1.2 mEq/L 0.43 to < 0.58 mmol/L	0.67 to < 1.04 mg/dL 0.6 to < 0.9 mEq/L 0.28 to < 0.43 mmol/L	< 0.67 mg/dL < 0.6 mEq/L < 0.28 mmol/L

CHEMISTRY				
	Grade 1	Grade 2	Grade 3	Grade 4
Hypophosphatemia				
Adult and Pediatric	2.0 to < LLN mg/dL	1.5 to < 2.0 mg/dL	1.0 to < 1.5 mg/dL	< 1.0 mg/dL
> 14 Years	0.63 to < LLN mmol/L	0.47 to < 0.63 mmol/L	0.31 to < 0.47 mmol/L	< 0.31 mmol/L
Pediatric 1 Year–14 Years	3.0 to 3.5 mg/dL	2.5 to < 3.0 mg/dL	1.5 to < 2.5 mg/dL	< 1.5 mg/dL
	0.96 to 1.12 mmol/L	0.80 to < 0.96 mmol/L	0.47 to < 0.80 mmol/L	< 0.47 mmol/L
Pediatric < 1 Year	3.5 to 4.5 mg/dL	2.5 to < 3.5 mg/dL	1.5 to < 2.5 mg/dL	< 1.5 mg/dL
	1.12 to 1.46 mmol/L	0.80 to < 1.12 mmol/L	0.47 to < 0.80 mmol/L	< 0.47 mmol/L
Hyperbilirubinemia				
Adult and Pediatric	> 1.0 to 1.5 × ULN	> 1.5 to 2.5 × ULN	> 2.5 to 5.0 × ULN	> 5.0 × ULN
> 14 Days				
Infant, ≤ 14 Days (non-hemolytic)	NA	20.0 to 25.0 mg/dL 342 to 428 µmol/L	> 25.0 to 30.0 mg/dL > 428 to 513 µmol/L	> 30.0 mg/dL > 513 µmol/L
Infant, ≤ 14 Days (hemolytic)	NA	NA	20.0 to 25.0 mg/dL 342 to 428 µmol/L	> 25.0 mg/dL > 428 µmol/L
Blood Urea Nitrogen	1.25 to 2.50 × ULN	> 2.50 to 5.00 × ULN	> 5.00 to 10.00 × ULN	> 10.00 × ULN

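### Serum phosphate, which triggers the Section 7.5.5 renal work-up, is not scheduled at five of Group 1's nine post-baseline renal visits

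*Protocol*

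**What the plan says.** **The rule.** Protocol Section 7.5.5 acts on a confirmed serum phosphate below 3.0 mg/dL. It applies to both groups: "in any paediatric patient receiving Tenofovir DF, renal function should be re-evaluated within one week". It names blood glucose, blood potassium and urine glucose as parts of that re-evaluation.

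**The renal panel.** Appendix 2 defines serum renal chemistry as "glucose, creatinine, creatinine clearance (calculated), magnesium, bicarbonate, chloride, potassium, sodium". The visit sections for Group 1 list the same items: Section 6.4.1 (Week 4), "Serum renal chemistry (creatinine, glucose, creatinine clearance (calculated), magnesium, bicarbonate, chloride, potassium, sodium), fasting required"; Section 6.4.2 (Weeks 12 and 36), "Group 1: Serum renal chemistry (creatinine, glucose, creatinine clearance (calculated), magnesium, bicarbonate, chloride, potassium, sodium), fasting required"; Section 6.4.5 (Weeks 60 and 84), "Group 1: Serum renal chemistry (glucose, creatinine, creatinine clearance (calculated), magnesium, bicarbonate, chloride, potassium, sodium), fasting required". The Synopsis and Section 3.2 agree. None includes phosphate.

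**The bone panel.** Serum phosphorus appears here only. Section 6.4.3 (Weeks 24 and 72) reads "Group 1 Only: Serum bone chemistry (calcium, phosphorus, 1,25 hydroxy vitamin D, PTH, osteocalcin, bone alkaline phosphatase, N and C telopeptides), fasting required". Sections 6.4.4 and 6.4.6 give the bone panel to both groups at Weeks 48 and 96.

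**Urine.** The urinalysis done at every Group 1 renal visit includes urine phosphate, but Section 7.5.5 acts on the serum value.

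**The concern.** Group 1 is the enhanced arm. Section 3.2 describes the study as a test of whether more frequent serum and urine testing and DEXA bring bone or renal changes to light earlier. The toxicity section has dedicated renal rules for two serum measurements: creatinine (with clearance) in 7.5.4 and phosphate in 7.5.5. Creatinine follows the enhanced renal schedule; phosphate follows the sparser bone schedule. At five visits Group 1 therefore has the three follow-up tests that 7.5.5 asks for, but not the scheduled result that would call for them.

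The protocol itself treats low phosphate as a tubular signal. Section 1.4 cites it as an example of the reactions for which 4 of 89 children in a paediatric HIV trial stopped tenofovir DF by 144 weeks. In the adult hepatitis B series described there (tenofovir DF and/or adefovir), all seven affected patients had low phosphate, while the other signs varied. At stake is a later start to the work-up in a paediatric safety study, and an enhanced schedule that is less enhanced than it appears for one renal marker.

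**Working it through.** The check compares visit lists; the plan states no figure to reproduce. Inputs are the Synopsis, Section 3.2, Sections 6.4.1 to 6.4.6 and Appendix 2. All counts are post-baseline.

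| | Weeks | Count |
|---|---|---|
| Group 1, serum renal chemistry | 4, 12, 24, 36, 48, 60, 72, 84, 96 | 9 |
| Group 1, serum phosphorus (bone panel) | 24, 48, 72, 96 | 4 |
| Group 1, renal visit without serum phosphorus | 4, 12, 36, 60, 84 | 9 − 4 = 5 |
| Group 2, serum phosphorus (bone panel) | 48, 96 | 2 |

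**Timing in Group 1.** Baseline phosphorus is scheduled. The longest interval between scheduled values is then 24 weeks, and the first on-treatment value is at Week 24. Through Week 48, 2 of 5 renal visits (Weeks 24 and 48) carry phosphorus. With phosphorus added at the five missing weeks, coverage is 9 of 9, the first value is at Week 4 and the longest interval is 12 weeks. The scheduled count, Group 1 to Group 2, goes from 4 to 2 now to 9 to 2.

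**Do the toxicity grades cover the same range?** Entry is at 12 to under 16 years, so two age bands of Appendix 4 apply.
- At 1 to 14 years, "2.5 to < 3.0 mg/dL" is Grade 2.
- Above 14 years, 2.0 mg/dL up to the lower limit of normal is Grade 1.
- For both grades, Section 7.5.1 says "Continue Tenofovir DF at the discretion of the investigator". That settles whether the drug continues; it does not order a work-up.

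For values just under 3.0 mg/dL, 7.5.5 is thus the rule that supplies a threshold, a one-week deadline and named tests.

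**How often might the rule fire?** Section 1.2.3.1 reports that no subject in the adolescent hepatitis B trial had confirmed phosphorus below 2 mg/dL by Week 72; 52 were randomised to tenofovir DF. Assuming all 52 were assessed, the exact 95% upper limit is 1 − 0.025^(1/52) = 0.068, or 6.8%. That cut-off is stricter than 3.0 mg/dL, so the frequency below 3.0 could be higher; the documents give no figure for it. Section 1.4 also gives hypophosphatemia rates from a paediatric HIV cohort (4.3 per 100 person-years on tenofovir DF, 0.9 in controls). The population differs and the cut-off is not stated. Those rates would in any case describe all cases, not cases delayed by this gap, so I do not convert them into an expected count.

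**The case against.** The case for leaving the plan alone has real substance.

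- **The rule does not require a scheduled sample.** Any confirmed result counts, and outside the enhanced schedule Group 1 is managed by local standards (Section 3.2). A reader might infer that 7.5.5 cannot fire at the five visits. The documents do not support that; they show only that no protocol-scheduled test can fire it there.
- **Tubular injury is not invisible at these visits.** Serum bicarbonate and potassium, and urine glucose, protein and phosphate, are all collected, and the opening of Section 7.5 requires abnormal laboratory findings to be investigated for cause. A reader might infer that the five visits are blind to tubular toxicity; they are not.
- **The event may be rare in this age group.** Section 1.4 places the proximal tubulopathy cases of the paediatric HIV trial at 2 to 12 years and reports none in the parallel adolescent trial. Section 8.9 says the adolescent hepatitis B trial had seen no renal adverse drug reaction by Week 72.
- **Phosphate on the bone schedule is already enhanced**, at 24-week against 48-week intervals.

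All four stand as limits on the size of the problem. None removes the mismatch. The general duty to investigate needs an abnormal result to act on, and a low phosphate that is not measured supplies none. In the adult series, low phosphate was the one sign present in every affected patient, so the other markers are not a full substitute.

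**Conclusion.** The mismatch is real and limited. Group 1 has a protocol-scheduled serum phosphate at 4 of its 9 post-baseline renal visits, the first at Week 24. The rule that depends on this value applies throughout treatment, and its named follow-up tests are already collected at all nine visits. It is worth correcting because the remedy is small and falls squarely on what the enhanced arm is meant to do. No claim is made about how many cases would be missed or delayed. The count of visits assumes the panel lists are complete as written; the remark in the Synopsis and Section 3.2 that the Group 1 renal schedule follows the SmPC does not add an analyte.

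A reader might extend the point to Section 7.5.4, which calls for clearance at each visit while Group 2's only fixed post-baseline creatinine is at Week 96. Since SAP Section 2.1 reports two completers, the reader might conclude that at most two Group 2 subjects had a scheduled creatinine. The documents do not establish this. Clearance can be calculated only where creatinine exists, and local testing is the intended comparator in Group 2. Section 6.4.6 can be read as giving early stoppers the full Week 96 panel without a group limit.

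**What to change.** Add a separate row to Appendix 2, serum phosphorus for Group 1, at Weeks 4, 12, 36, 60 and 84. Add serum phosphorus to the Group 1 blood samples in Sections 6.4.1, 6.4.2 and 6.4.5, with matching text in the Synopsis and Section 3.2.

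Leave the shared definition of serum renal chemistry alone. It serves both groups, and Group 2 has that panel at Screening, Baseline and Week 96. Editing it would add a Screening phosphate in both groups and list phosphorus in two panels wherever they coincide. A separate row keeps the Group 2 comparator as it is.

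**Cost.** Five extra assays per Group 1 subject on blood already drawn, so 5 × 50 = 250 for the planned group, plus any repeat tests and one-week work-ups they set off. No visit or blood draw is added for the scheduled assays. SAP Section 2.1 shows that follow-up has ended, so the change applies to the protocol as designed and cannot recover values that were not measured.
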